Population: all patients belonging to the Chemotherapy ward will be recruited consecutively for a new antineoplastic treatment protocol. The process of informing and collecting the participants' consent will take place during the first admission in which intravenous administration of the chemotherapy will be started. Potential participants will be identified / selected for recruitment through inclusion and exclusion criteria described below. Enrolled patients who will not continue the chemotherapy protocol within our Institute but at another facility will exit the study.

Inclusion criteria:

all patients diagnosed with bone tumors who start a new chemotherapy treatment protocol, both on admission and on an outpatient basis at the Chemotherapy ward for its antineoplastic treatment over 12 years of age. The NCCN Guidelines Cancer-Related Fatigue identifies appropriate screening with rating scales with scores from 0 to 10 precisely for patients older than 12 years.

Exclusion criteria:

patients with little knowledge of the Italian language due to the impossibility of completing the assessment scales.

Primary outcome:

the patient's Fatigue will be measured during the treatment period with antineoplastic drugs and part of the followup period. To this end the BFI scale validated in Italian will be used (Mendoza et al 1999; Catania et al, 2013) which includes 9 items with a score for each of 0 to 10 and a consequent total score from 0 to 90. The measurement will take place in 4 times: the day of enrollment, 6 months, 12 months and 24 months after enrollment.

Secondary outcome:

the quality of life of patients measured by the EORTC QLQ C-30 scale (Aaronson et al, 1993) and the level of autonomy measured by the TESS scale (Davis et al, 1996) in 4 steps: the enrollment day , at 6 months, at 12 months and at 24 months from enrollment.

Variables taken into consideration: through the literature search and the comparison between professionals of different disciplines (nurses, physiotherapists, oncologists) involved, a panel of variables was established to collect:

- Age
- sex
- BMI
- Smoking
- diabetes

- cardiopathies (hypertension, previous heart attack, ...)
- Comorbidity (pulmonary, renal, anemia, arthritis, neuromuscular complications, sleep disorders, pain, emotional distress)
- Diagnosis,
- presence of metastases at the entrance

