number of therapy cycles	OBSERVATION sheet (CRF): to be found in health documentation and then in the calculation sheet)	Nurse
tumor location	Enrollment form: to be reported in the calculation sheet	Nurse
surgery (date and type)	OBSERVATION sheet (CRF): report in a calculation sheet	Nurse
Pain	Measured with NRS scale. Data present in the BFI Sheet: to be reported in the calculation sheet	Nurse
Autonomy level	TESS scale: self-filled by the patient (6-12-24 months from enrollment)	Physiotherapist

Statistical analysis: The characteristics of the sample will be described using the mean and standard or median deviation and interquartile range for quantitative variables and absolute and percentage frequencies for qualitative variables. Simple and multiple linear regression analyzes will be performed and to identify predictors of primary and secondary outcome.

Sample size: In a pilot study of 19 patients at the Chemotherapy SSD the average BFI score was 31.6 with DS 19.1 at a mean follow-up of 5.2 months and DS 3.7. On the basis of this data, the number of variables taken into consideration equal to 15 in a multiple linear regression, an effect size of 0.1, an alpha value of 0.05 and a power of 80% the

number of patients to be enrolled is equal to 183. The sample size was calculated with Stata 15.0.

Duration of the study: The project lasted 5 years as follows:

Month 1-3 Meeting and training of the team involved in the study

Months 3–36 Patient enrollment and data collection.

Months 36-48 Construction of the database and preliminary analysis

Months 48-60 Follow-up and Statistical analysis of data

The approval date of the Ethics Committee will be considered as the starting date of the trial.

Safety assessment: as this is an observational study, patients will be treated in accordance with the rules of good clinical practice and in accordance with the protocols regularly used in the operating unit involved.

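### The last 24-month assessment falls in month 60, when the analysis and the project end, leaving no time for cleaning, lock and final analysis

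*Protocol*

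**What the plan says.** The protocol's section on the duration of the study sets a 60-month project ("The project lasted 5 years as follows") and fixes time zero: "The approval date of the Ethics Committee will be considered as the starting date of the trial". After three months of team preparation, the timetable has three rows:

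- "Months 3–36 Patient enrollment and data collection"
- "Months 36-48 Construction of the database and preliminary analysis"
- "Months 48-60 Follow-up and Statistical analysis of data"

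Under the primary outcome, the BFI schedule is: "The measurement will take place in 4 times: the day of enrollment, 6 months, 12 months and 24 months after enrollment". The secondary outcome section sets the same four times for the QLQ-C30 and TESS, and the data collection table repeats them.

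**The concern.** Each patient's schedule runs for 24 months, and enrolment is open until month 36. Follow-up therefore continues without a break to month 60, and two things in the timetable do not match this.

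First, follow-up and the final analysis share the last row and end together. An analysis of complete data cannot start until the last 24-month visit has been made and the database locked, and by then the project is over.

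Second, the first of the three rows names data collection and the last names follow-up, but the row between them names neither, although visits of all three kinds fall due in it.

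At stake are the 24-month values of the latest-enrolled patients. The objective is to describe how fatigue and quality of life evolve through treatment and early follow-up, and 24 months is the last of the four time points. If the analysis is finished on schedule, these values are the ones left out.

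**Working it through.** **Inputs from the protocol.** Enrolment in months 3 to 36, a 33-month window. Post-enrolment visits at 6, 12 and 24 months. Project end at month 60. Sample size section: 183 patients, 15 variables, effect size 0.1, alpha 0.05, power 80%.

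**Assumptions.** Uniform accrual over the window and no drop-out. The protocol gives no accrual pattern or drop-out rate.

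**Step 1. The protocol's own figure.** For the overall F test in a multiple linear regression with 15 predictors, power = P[F′(15, N − 16, λ) > F crit], where λ = N × R²/(1 − R²).

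- Reading 0.1 as R², λ = 183 × 0.1/0.9 = 20.3 and power is 80.3%. N = 183 is the smallest size that reaches 80%, so the stated figure is reproduced.
- Reading 0.1 as Cohen's f² would require 201. The R² reading is therefore used below.

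**Step 2. The last visit.** This needs no accrual assumption, only that enrolment uses its whole window. A patient enrolled in month 36 is due at months 36 + 6 = 42, 36 + 12 = 48 and 36 + 24 = 60. No visit falls after month 60, and no month remains after the last one.

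**Step 3. Visits due in months 36-48.**

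| Visit | Enrolment months concerned | Share |
|---|---|---|
| 6 months | 30-36 | 6/33 = 18% |
| 12 months | 24-36 | 12/33 = 36% |
| 24 months | 12-24 | 12/33 = 36% |
| All post-enrolment visits | | 30/99 = 30% |

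With 183 patients this is about 166 of 3 × 183 = 549 visits. Moving the enrolment window's edges (start at month 1 or 4, or end at month 35) changes the overall share only to between 28.6% and 31.3%. A further 12/33 = 36% of the 24-month visits, about 67, fall in months 48-60.

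**Step 4. 24-month values available at a data cut.** At month m the share is (m − 24 − 3)/33. Power uses the formula of Step 1 with R² = 0.10.

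| Cut at month | Share of 24-month values | Patients of 183 | Power of a 24-month BFI regression |
|---|---|---|---|
| 48 | 21/33 = 64% | about 117 | 53% |
| 54 | 27/33 = 82% | about 150 | 69% |
| 57 | 30/33 = 91% | about 166 | 75% |
| 60 | 33/33 = 100% | 183 | 80% |

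**Step 5. The earlier time points.** The last 6-month visit is due at month 42 and the last 12-month visit at month 48. From month 48 on, the 6- and 12-month outcome values are complete under the same assumptions.

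**The case against.** The strongest reply is that the timetable is a list of milestones and does not exclude anything it fails to mention. Visits are timed from each patient's enrolment, and data are collected whenever the patient is admitted or attends the outpatient service. Nothing says that collection stops at month 36. This stands. The silence of the months 36-48 row is most likely loose wording, and the 30% is the share of visits falling in a badly labelled row, not a forecast of lost data.

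Four stronger readings are tempting, and the protocol does not support them.

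- *The timetable cannot hold the 24-month visit.* It can. Month 60 lies on the boundary, and the last row names follow-up.
- *The study has only 53% power.* That figure requires the final analysis to be cut at month 48, the first moment of a 12-month row. The protocol sets no such cut-off and calls the earlier work preliminary. It is one end of a range.
- *The sample falls below the 183 that was planned for.* The sample size is not tied to the 24-month BFI. No time point is named for the regression, and the pilot data came from a mean follow-up of 5.2 months.
- *The trajectory is biased.* Omitting late visits because of the calendar date biases the trajectory only if later enrollees differ from earlier ones, and nothing in the document indicates that.

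The reply leaves the end of the schedule untouched. However the middle row is read, 36 + 24 = 60 leaves no time between the last visit and the end of the project.

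**Conclusion.** The point holds as a scheduling conflict within the protocol. With enrolment to month 36, the last 24-month BFI, QLQ-C30 and TESS fall in the month in which both analysis and project end. A final analysis completed on schedule must therefore leave out the 24-month data of the latest enrollees.

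How much is lost depends on the date of the data cut. For cuts from month 48 to month 57, between 36% and 9% of the 24-month values would be missing, and power for a regression on the 24-month BFI would lie between 53% and 75%. These figures rest on uniform accrual, no drop-out and the R² reading of the effect size. The conflict itself rests only on the stated dates and on enrolment using its full window. The unlabelled months 36-48 are a matter of wording to be clarified.

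**What to change.** Amend the timetable in two places.

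1. State that the 6-, 12- and 24-month visits continue through months 36-60, so that the months 36-48 row cannot be read as a pause in collection.
2. Place the final analysis after the last 24-month visit and database lock, and extend the stated project duration a few months beyond month 60. If 3 to 6 months were needed (an assumption, since the protocol gives no figure), the project would end at month 63 to 66.

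Closing enrolment earlier by the same number of months would also create the room, but with less time to reach 183 patients. The preliminary analysis can stay as planned.

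The cost of the extension is a protocol amendment and a slightly longer project. No extra patients or visits are needed.
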